### 9.2 Data analysis

Fisher Exact tests will be used to compare the incidence of the composite primary endpoint, Durable Treatment Response, Relapse, treatment-related adverse events and 4-week, 1-year and 2-year incidence of death between the treated group and historical controls. We will consider Chi-Square test to examine differences in the type and severity of adverse events between the treated group and historical controls.

The time to Durable Treatment Response and Relapse will be described by Kaplan-Meier estimators and log rank tests. The effects of patient characteristics will be evaluated with Cox proportional hazards models. Numbers of plasma exchanges to Durable Treatment Response will be compared with non-parametric tests (e.g. Kruskal-Wallis analysis of variance).

The value of ADAMTS13 biomarker data for predicting Exacerbation, Durable Treatment Response or Relapse will be analyzed by logistic regression. The relationship between ADAMTS13 biomarker parameters and platelet count, LDH or B cell levels will be investigated with linear regression models.

Rituximab levels and the extent of B cell depletion will be analyzed as stratified categorical data with Cochran-Mantel-Haenszel statistics.

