## 7.2 Relatedness to Participation in the Research Study

Each AE should be evaluated as to whether it was related or possibly related to participation in the research study (meaning that there is a reasonable possibility that the AE may have been caused by the procedures involved in the research). AEs determined to be solely caused by an underlying disease, disorder, or condition of the subject; or other circumstances unrelated to the research should be categorized as being not related to participation in the research.

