## 7.3 Relatedness to Use of the Study Drug (Rituximab)

Each AE should also be evaluated as to whether it was related to the use of rituximab:

Definite	An AE is clearly related to use of rituximab
Probable	An AE has a strong temporal relationship to use of rituximab, and another etiology is significantly less likely.
Possible	An AE has a strong temporal relationship to use of rituximab, and an alternative etiology is equally or less likely.
Unlikely	An AE has little or no temporal relationship to use of rituximab, and/or a more likely alternative etiology exists.
Not Related	An AE is not related to use of rituximab (no temporal relationship, or a much more likely alternative etiology exists).

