## 7.4 Reporting and Monitoring Adverse Events

Information about all adverse events that occur within 1 year after enrollment in subjects will be collected. The clinical course of AEs will be followed until a medical outcome is determined. Additional information that becomes available may be added to previously submitted AE reports at any time. Site investigators should follow their local IRB's guidelines in terms of reporting AEs to them. All AEs must be reported to Washington University's Clinical Coordinating Center (CCC) on designated case report forms (CRFs) to be provided by the sponsor-investigator.

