### 7.4.1 Expedited Reporting of Serious Adverse Events

Serious adverse events (SAEs) are defined as AEs that cause death, a life-threatening adverse experience, or a persistent or significant disability/incapacity (i.e. Grade 4 and 5 events); inpatient hospitalization or prolongation of existing hospitalization; pregnancy abortion, or a congenital anomaly, birth defect, or cancer in a neonate/infant born to a female subject.

Serious adverse events must be reported by Clinical Center personnel to the Washington University CCC within 24 hours of the Clinical Center's awareness (Monday-Friday) by electronically mailing the completed Serious Adverse Event form and de-identified source documentation to [name] ([[contact]](mailto:[contact])) and [name], BSN ([[contact]](mailto:[contact])). Each Clinical Center will follow their local IRB reporting policy of AEs and SAEs. If a SAE is determined to be unexpected and possibly, probably, or definitively related to rituximab or to participation in the research study, it must be reported to the local IRB within 24 hours of the Clinical Center's awareness of the event. Data on all serious adverse events that occur in subjects will be collected through the end of their study participation (i.e. the full 2-year follow-up period).

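### Treatment-related adverse events are tested against historical controls, but the plan's collection and attribution rules cover only enrolled patients, so there is no comparable control count

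*Combined protocol and SAP*

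**What the plan says.** Section 1.2.1 lists the incidence, type and severity of treatment-related adverse events as a secondary endpoint. It does not say which treatment is meant. For the analysis, section 9.2 states: "Fisher Exact tests will be used to compare the incidence of the composite primary endpoint, Durable Treatment Response, Relapse, treatment-related adverse events", together with death at three fixed times, between the treated group and historical controls. It adds: "We will consider Chi-Square test to examine differences in the type and severity of adverse events between the treated group and historical controls".

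The collection rules are in section 7, which adopts CTCAE version 4.0 grading. Section 7.4: "Information about all adverse events that occur within 1 year after enrollment in subjects will be collected". Section 7.4.1: "Data on all serious adverse events that occur in subjects will be collected through the end of their study participation", which it equates with the 2-year follow-up. Under section 4.1 enrollment requires signed consent, so the historical controls are not subjects in this sense.

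There are two relatedness judgements. Section 7.2: "Each AE should be evaluated as to whether it was related or possibly related to participation in the research study". Section 7.3: "Each AE should also be evaluated as to whether it was related to the use of rituximab".

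The controls are described in the Abstract as treated initially with plasma exchange and corticosteroids, and in section 9.1 as 40 reviewed patients at one hospital who would have met the inclusion criteria. Neither place gives a source, window or grading rule for their adverse events, or the length of their follow-up.

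On relapse, section 9.2 also plans a time-to-event analysis: "The time to Durable Treatment Response and Relapse will be described by Kaplan-Meier estimators and log rank tests".

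**The concern.** A two-group test of incidence needs the same event, looked for in the same way over the same time, in both groups. Here the treated numerator comes from prospective graded collection with a formal attribution step. The control numerator has no stated source, and neither attribution scale fits a control. Relatedness to research participation cannot apply to someone who was not in the research. Relatedness to rituximab can apply only to a control who received it, for example as salvage, which section 2.4 calls the current standard of care at standard dose. In that case low-dose adjuvant use would be set against standard-dose salvage use.

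The Abstract calls this a pilot safety/efficacy study. A significant Fisher result could be read as excess toxicity of low-dose rituximab when it reflects only that control events were not recorded or could not be called related.

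The lesser point is that relapse is tested as ever/never with no horizon, whereas death in the same sentence has three. If controls were followed for a different length of time from treated patients, the ever/never proportions differ even with identical hazards.

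**Working it through.** **Inputs.** From section 9.1: 20 treated, 40 controls, 5% level (taken as two-sided). From section 2.1, for illustration only: about 30% relapse within 2 years. Event risks, the share of control events on record, and control follow-up are not in the documents; they are assumed and varied.

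**The plan's own figure.** The plan gives no number for this comparison. Its sample size reproduces. With 55% in 40 and 10% in 14, the pooled proportion is (22 + 1.4)/54 = 0.433, the null SE is 0.1539 and the alternative SE is 0.1123. Power is Φ[(0.45 − 1.96 × 0.1539)/0.1123] = Φ(1.32) = 90.7%, and 13 patients give 88.8%. That calculation concerns the primary endpoint and is untouched by this point.

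**Reading 1: treatment-related means rituximab-related, and no control had rituximab.** Controls are 0/40 by construction. With three events in all, the two-sided Fisher p-value for 3/20 v 0/40 is C(20,3)/C(60,3) = 1140/34220 = 0.033. For 2/20 it is 0.107 and for 4/20 it is 0.010. One control event changes the picture: 3/20 v 1/40 gives (1140 × 40 + 4845)/487635 = 0.103.

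**Reading 2: plasma-exchange and steroid toxicity (sections 7.1.3 and 7.1.4) also count.** Let both groups have true risk r and let a fraction c of control events be on record. The rejection rate is the sum, over all tables (a, b) with Fisher p ≤ 0.05, of Bin(a; 20, r) × Bin(b; 40, rc).

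| True risk r | c = 100% | 90% | 75% | 50% | 25% |
|---|---|---|---|---|---|
| 10% | 2.8% | 3.3% | 4.7% | 9.2% | 17.6% |
| 20% | 3.5% | 4.0% | 6.2% | 16.8% | 40.9% |
| 30% | 3.6% | 4.3% | 7.4% | 22.4% | 57.9% |
| 70% | 3.6% | 5.8% | 19.5% | 65.9% | 98.1% |

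At r = 30%, the part of the rejection rate that goes against rituximab is 2.0%, 3.4%, 7.1%, 22.3% and 57.9%, so almost all of the excess lies in that direction.

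**Relapse.** Take the same hazard in both groups, 30% risk at 24 months, treated patients followed for 24 months and controls for m months. Control risk is 1 − exp[−H(m/24)^k], with H = −ln 0.7.

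| m (months) | 12 | 24 | 36 | 48 |
|---|---|---|---|---|
| Fisher, constant hazard (k = 1) | 18% | 3.6% | 10% | 27% |
| Fisher, declining hazard (k = 0.5) | 8% | 3.6% | 5% | 8% |

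The error goes against rituximab at 12 months and in its favour at 36 and 48. The planned log-rank test, censored at 24 months, rejects 4.6% to 5.2% of the time across these cases and also with control follow-up spread uniformly over 3 to 24 months (simulation, 20,000 replicates each).

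**The case against.** The strongest reply is that treatment-related need not mean rituximab-related. Section 7 lists plasma-exchange and corticosteroid toxicities, section 7.4.2 asks the Medical Monitor to weigh all three treatments, and controls had plasma exchange and steroids. That stands. A reader might infer that the control count must be zero; the documents support this only on the narrow reading with no rituximab in any control. The broad reading does not rescue the test, because the plan still has no attribution scale for those treatments and no rule for finding control events.

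A reader might also infer that background toxicity will routinely be scored as rituximab-related in treated patients, because the Possible category allows a case where there is a competing cause: "and an alternative etiology is equally or less likely". The same category also requires a strong temporal relationship to rituximab, and the documents give no rate for such events. No false-positive rate is therefore claimed on that basis.

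The capture fractions have no source in the documents. That is true, and at 10% to 30% risk with 90% or more on record there is no inflation above 5%. It would be wrong to generalise: at 90% capture the rate is 5.8% when the true risk is 70%, and 9.7% when it is 90%.

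The chi-square test is only under consideration, the endpoints are secondary, no decision rule hangs on them, and under-recording in controls produces a false alarm rather than hidden harm. All of this stands and limits the severity.

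On relapse, the log-rank test in the same section already handles unequal follow-up. That is why the point is minor. A reader might infer that the relapse analysis as a whole is unsound; it is not.

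**Conclusion.** The concern holds for the adverse-event comparison. Followed as written, section 9.2 compares a prospectively collected and attributed count with one the plan gives no means of constructing. This does not depend on any assumed figure. The size does: it runs from no inflation to most tests rejecting, according to the meaning of treatment-related, the true event risk and the share of control events on record. A moderate illustration is 22% rejection at 30% risk and 50% capture, against 3.6% with full capture.

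The documents do not show that control events were in fact missed, or that the trial will report false toxicity; control ascertainment is simply not stated.

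The missing relapse window is a small defect, since the better test is already planned. The primary endpoint and the sample size are not affected by either part. The change should be made, but it is not a bar to the trial.

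**What to change.** **Adverse events.**
- Remove the Fisher and chi-square tests against historical controls.
- Report treated-arm rates with exact (Clopper-Pearson) 95% confidence intervals, all adverse events to 1 year and serious adverse events to 2 years. For scale, 0/20 has an upper bound of 1 − 0.025^(1/20) = 16.8%, and 3/20 has an interval of 3.2% to 37.9%.
- Show events possibly, probably or definitely related to rituximab, the grouping already used in sections 7.4.2 and 7.4.4, separately from all adverse events. Plasma-exchange and steroid toxicity then stays visible.
- Limit between-group safety comparison to outcomes ascertained the same way over the same window in both groups, such as the deaths already planned at 4 weeks, 1 year and 2 years.

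**Relapse.**
- Use the planned Kaplan-Meier and log-rank analysis as the comparison, and report the 2-year estimate with a 95% confidence interval in each group.
- Censor both groups at last contact or 24 months from one stated origin. The Definitions count Relapse from Treatment Response but the Observation Period from first Durable Treatment Response, so the origin must be named.
- Report the controls' median and range of follow-up, and state that log-rank does not correct for differences in how relapse was detected.

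**Cost.** Changes to the analysis text only, with no new visits or samples. Control last-contact dates must be abstracted, but the planned Kaplan-Meier analysis needs them anyway. The price is that there is no between-group p-value for adverse events, and control relapses after 24 months go unused.

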## DEFINITIONS

**Day 1:** The first day a subject receives plasma exchange for treatment of TTP.

**Treatment Response:** 2 consecutive days with platelet count  $\geq 150,000/\mu\text{L}$

**Durable Treatment Response:** Treatment Response that persists for  $\geq 30$  days after discontinuation of plasma exchange.

**Exacerbation:** Recurring TTP  $\leq 30$  days after a Treatment Response and discontinuation of plasma exchange.

[figure not shown]
**Refractory TTP:** Failure to achieve a Treatment Response by day 28, or failure to achieve a Durable Treatment Response by day 60.

**Composite Primary Endpoint:** Exacerbation or Refractory TTP.

**Relapse:** Recurring TTP  $> 30$  days after Treatment Response.

**Observation Period:** The interval of 2 years after a subject first achieves a Durable Treatment Response.

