### 1.2 Secondary Endpoints

#### 1.2.1 Clinical and Safety Endpoints

- Incidence of Durable Treatment Response
- Number of days to Durable Treatment Response
- Number of plasma exchanges to Durable Treatment Response
- Incidence of relapse
- Numbers of days to relapse
- 4 week, 1 year and 2 year incidence of death
- Incidence, type and severity of treatment-related adverse events

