months). Of eight patients with available ADAMTS13 data after rituximab treatment, seven had recovery of normal ADAMTS13 activity and disappearance of a detectable inhibitor (Ling 2009).

A prospective study in France (Froissart 2012) compared 22 adults with refractory TTP treated with rituximab and plasma exchange to 53 historical controls who received plasma exchange with or without vincristine. The time to a durable remission was significantly shorter for patients receiving rituximab ( $P = 0.03$ ), although the plasma volume required to achieve a durable remission was not significantly different compared to controls. Of the rituximab-treated patients, none relapsed within the first year although three relapsed up to 3 years later. Treatment with rituximab produced a rapid and profound depletion of peripheral B-cells that lasted 9 months and correlated with a higher level of ADAMTS13 activity and lower antibody titers. These differences were no longer significant after 12 months. No severe side effects occurred.

Thus, treatment with rituximab normalizes ADAMTS13 and induces durable remissions in >90% of patients with refractory or relapsing TTP. Late relapses have occurred in ~10% of these patients after 9 months to 4 years; all but one had a prolonged remission when retreated with rituximab (Sadler 2008). These results suggest that adjuvant rituximab might increase the rate of remission and reduce relapses for patients with severe ADAMTS13 deficiency at diagnosis. In fact, a recent study of adjuvant full dose rituximab (375 mg/m^2 weekly x 4) observed a 10% relapse rate compared to 57% in historical controls (Scully 2011).

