### 5.2.5 Treatment of Refractory TTP

The subject will be considered to have Refractory TTP if they do not have a Treatment Response by day 28, or do not have a Durable Treatment Response by day 60. The treatment of Refractory TTP will include resuming plasma exchange and corticosteroids. Additional salvage therapy is at the physician's discretion and can include full dose rituximab  $375 \text{ mg/m}^2$  weekly for 4 doses. Patient with Refractory TTP will be followed for 2 years with laboratory monitoring.

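### The Fisher test of Durable Treatment Response incidence has no time point and no salvage rule, so late responses on salvage count as successes and the comparison is hard to interpret

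*Combined protocol and SAP*

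**What the plan says.** The Definitions describe DTR as a "Treatment Response that persists for" at least 30 days once plasma exchange has stopped. No latest day is attached, and nothing excludes a response reached on further therapy. Section 1.2.1 lists the endpoint simply as "Incidence of Durable Treatment Response". Section 9.2 then plans: "Fisher Exact tests will be used to compare the incidence of the composite primary endpoint, Durable Treatment Response, Relapse, treatment-related adverse events". The same sentence gives death explicit time points: "4-week, 1-year and 2-year incidence of death between the treated group and historical controls". DTR gets none.

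Day 60 appears only in the definition of Refractory TTP (repeated in 5.2.5): "Failure to achieve a Treatment Response by day 28, or failure to achieve a Durable Treatment Response by day 60". For these patients 5.2.5 adds: "Additional salvage therapy is at the physician's discretion and can include full dose rituximab". They are followed for 2 years, and salvage is not among the off-study criteria in 8.2. The Observation Period is "The interval of 2 years after a subject first achieves a Durable Treatment Response", whenever that happens.

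Section 9.2 also plans Kaplan-Meier curves and a log-rank test for time to DTR. It does not say how salvage is handled there either.

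**The concern.** Read as written, a patient who fails the primary endpoint at day 60, receives full-dose rituximab, and later stays in response for 30 days off exchange is a DTR success. That success belongs at least partly to the salvage treatment and not to the adjuvant low dose under test.

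An ever/never comparison also depends on how long each group was watched and how often each was salvaged. Treated patients have protocol follow-up. The controls come from a review of 40 patients (9.1), and the abstract describes only their initial treatment. Section 2.4 calls salvage rituximab standard practice, but the documents give neither the share of controls who received it nor their follow-up for this endpoint.

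Two errors are possible. If salvage works well in both groups, a real early benefit largely disappears from the test. If salvage use or success differs between groups, a difference can appear that owes nothing to the adjuvant drug.

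**Working it through.** **Inputs.** From 9.1: composite failure 55% in controls and 10% assumed in treated patients, 40 controls, 14 treated needed, 20 to be enrolled, 5% significance level (sidedness not stated; two-sided taken). From 2.2: rituximab "induces durable remissions in >90% of patients with refractory or relapsing TTP". From 2.1: about 80% survival with plasma exchange. Not in the documents: any DTR rate, the share of controls salvaged, or a power statement for DTR.

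**1. The plan's own figure.** Pooled normal approximation, 14 treated vs 40 controls:
- pooled proportion = (40 × 0.55 + 14 × 0.10)/54 = 0.4333
- SE under the null = √[0.4333 × 0.5667 × (1/40 + 1/14)] = 0.1539
- SE under the alternative = √[0.55 × 0.45/40 + 0.10 × 0.90/14] = 0.1123
- power = Φ[(0.45 − 1.96 × 0.1539)/0.1123] = 90.7%

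With 13 treated it is 88.8%, so 14 is reproduced. Exact two-sided Fisher power for the composite is 84.2% at 14 treated and 94.8% at the planned 20.

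**2. DTR at any time.** A patient with neither exacerbation nor Refractory TTP has reached DTR by day 60. Let s be the share of composite failures who reach DTR later, taken as equal in both groups. Then

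DTR incidence = 1 − F(1 − s), with F = 0.55 (controls) or 0.10 (treated).

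Exact two-sided Fisher power, 20 vs 40, by enumeration of both binomials:

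| s | Controls | Treated | Power |
|---|---|---|---|
| 0.90 | 94.5% | 99% | 0.1% |
| 0.80 | 89% | 98% | 4.6% |
| 0.70 | 83.5% | 97% | 20.1% |
| 0.60 | 78% | 96% | 39.6% |
| 0.50 | 72.5% | 95% | 55.5% |

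**3. A cap from deaths.** If control DTR is instead limited to the 80% survival figure and treated DTR is 90% to 100%, power is 11.5% to 56.3%.

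**4. What significance would need.** Even with 20/20 treated responders, at least 8 of 40 controls must never reach DTR: 8/40 gives p = 0.043, 7/40 gives p = 0.084.

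**5. A false difference.** Suppose the adjuvant drug does nothing, so that 45% in each group reach DTR by day 60, and later success among failures is 90% in treated patients but 50% in controls (an assumption for illustration). Any-time DTR is 0.45 + 0.55 × 0.90 = 94.5% vs 0.45 + 0.55 × 0.50 = 72.5%. The test then declares a difference 52% of the time.

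**6. DTR by day 60.** Let f be the share of composite failures, such as exacerbations, who still reach DTR by day 60. The formula is that of step 2 with f in place of s:
- f = 0: 45% vs 90%, power 94.8%
- f = 0.2: 56% vs 92%, power 84.6%
- f = 0.5: 72.5% vs 95%, power 55.5%

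DTR needs 30 days off exchange, so DTR by day 60 requires exchange to end by about day 30. That suggests f is small, but the documents do not give it.

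**The case against.** **The power loss rests on assumptions.** A reader might infer that the test has almost no power on the protocol's own figures. The documents do not support that. The durable-remission figure above 90% describes rituximab in refractory or relapsing disease. The 0.1% applies it to every composite failure in both groups. Yet salvage is discretionary, exacerbations are first managed by restarting exchange and steroids (5.2.3), some failures may be deaths, and salvage among controls is unquantified. This objection stands: the result is a range, not a single figure.

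**Timing is analysed separately.** Time to DTR has its own log-rank test, and the number of exchanges to DTR is compared too. In a simulation of the 90% scenario (assumed timings: non-failures reach DTR on days 36 to 60, failures on days 61 to 120 or 61 to 365), log-rank power is about 87%, or 81% if late responses start from day 45. So the stronger inference that the effect on durable response would be lost, or that the DTR results would contradict the primary result, also fails. But the log-rank test uses the same definition without a salvage rule, and the Fisher comparison remains a separate planned test.

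**The replacement nearly repeats the primary test.** Failure to reach DTR by day 60 is already part of the composite. This is a fair cost. A patient being both a primary-endpoint failure and an eventual DTR success is also not a contradiction in itself: fewer early failures with similar eventual response is a coherent finding.

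**This is a pilot powered only for the composite.** Low power for one secondary test is not by itself a planning error. That is correct. The defect is that the comparison, as defined, does not isolate the adjuvant treatment.

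**Conclusion.** The gap is in the text and needs no assumption: the tested DTR incidence has no time point and no rule for responses after salvage. It should be closed, but it leaves the primary analysis and its sample size untouched.

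Its size depends on quantities the documents do not give. With equal later success in both groups, power runs from about 0.1% (90% of failures later reach DTR) to 55% (50% do). Throughout that range it is well below the 94.8% of the composite. With unequal later success, the test can point to an effect that is not there.

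Nor should a day-60 rule be read as guaranteeing 94.8% power. That is the upper bound, reached only if no composite failure attains DTR by day 60.

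**What to change.** In 1.2.1 and 9.2:
- Define the tested endpoint as DTR by day 60 without salvage therapy. Day 60 is already in the Refractory definition.
- Count death or salvage before then as no response.
- Say which treatments count as salvage for this endpoint, and whether exchange restarted for an exacerbation is among them.
- Apply the same rule to the historical controls.
- Report DTR at any time, including after salvage, descriptively for each group.
- State how salvage is handled in the time-to-DTR analysis.

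The cost is a few lines of text and no new data in treated patients. For the controls, dates of salvage and death up to day 60 must be available from the chart review. The main downside is that the endpoint largely overlaps with the complement of the primary composite, so it should be presented as supportive and not as independent evidence.

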### 1.1 Primary Endpoint

- Incidence of composite primary endpoint, Exacerbation or Refractory TTP

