## **3. STUDY POPULATION**

### **3.1 Inclusion criteria**

- 1) Age  $\geq$ 18 years
- 2) Diagnosis of suspected TTP
  - a. Platelet count of  $<80,000/\mu\text{L}$  for newly diagnosed patients and  $<120,000/\mu\text{L}$  for relapsed patients
  - b. Microangiopathic hemolytic anemia (MHA) with RBC fragmentation
  - c. LDH  $>1 \times \text{ULN}$
- 3) Subjects who will receive treatment for TTP with plasma exchange
- 4) Subjects who have not started the 5TH plasma exchange.
- 5) Plasma ADAMTS13 activity  $<10\%$

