#### 6.1.3 Baseline (Table 3)

After evaluation for eligibility, the following measurements will be taken at baseline. Data collected for baseline measurements are to be abstracted from the subject's medical record using the earliest information after admission for TTP. If a laboratory test is not included in the subject's record, it is to be obtained either by using extra serum or plasma collected prior to the first plasma exchange and retained in the clinical laboratory for possible clinical needs, or from initial waste plasma from the first plasma exchange.

1) Demographic and Medical History

- Weight and height
- Gender
- Ethnic origin
- Race
- History of TTP

- Date of onset of symptoms
- Date of first plasma exchange
- Previous plasma infusion prior to enrollment in study during this admission
- Past Medical History including: (see case report form for complete list)
  - Autoimmune disease (SLE, other)
  - Prior thrombotic disease (CVA, MI, DVT, Other)
  - Diabetes (Diet Controlled, Oral Antiglycemics, Insulin)
  - Hypertension (Medication Yes/No)

2) Surveillance panel

3) Peripheral smear

4) Coagulation panel

5) Reticulocyte count

6) Chemistry panel

7) Expanded chemistry panel

8) Other Laboratory

- DAT
- Serum IgG, IgM, and IgA
- Urinalysis with microscopic examination

9) ADAMTS13 activity and antibody (plasma samples will be sent to the Blood Center of Wisconsin and [name])

10) Samples for repository (drawn prior to any plasma exchange or rituximab treatment)

- Serum
- Citrated plasma
- Lithium-heparin plasma
- Packed cells

11) Assessment

- Documentation of clinical status on Baseline Visit CRF
- Documentation of medications on Concomitant Medications CRF
- Plasma Exchange log – for all plasma exchanges since admission

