## 9. STATISTICAL CONSIDERATIONS

### 9.1 Sample Size and Power

Review of 40 patients with TTP at BJH who would have met the inclusion criteria indicates that the composite primary endpoint rate was 55% in this historical group. Assuming a 10 percent of composite primary endpoint rate in the treated group and 40 historical controls, 14 treated patients are needed to have a 90% power to detect a 45 % difference in the incidence of exacerbation at the 5% significance level. We will enroll 20 patients total and expect to enroll 12 patients per year. Therefore, recruitment may be complete within less than 2 years. The time would be reduced by participation of other regional hospitals.

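### The primary Fisher test against historical controls does not adjust for the mix of newly diagnosed and relapsed patients, so a difference in mix could bias it in either direction

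*Combined protocol and SAP*

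**What the plan says.** - **Endpoint.** Section 1.1 gives the primary endpoint as "Incidence of composite primary endpoint, Exacerbation or Refractory TTP", a yes/no outcome per patient.
- **Test.** Section 9.2: "Fisher Exact tests will be used to compare the incidence of the composite primary endpoint", treated group against historical controls, with no strata and no covariates.
- **Population.** Section 3.1, criterion 2a, sets a platelet ceiling of 80,000/µL for newly diagnosed patients and 120,000/µL "for relapsed patients". Both types are eligible.
- **Controls.** Section 9.1: "Review of 40 patients with TTP at BJH who would have met the inclusion criteria", and "the composite primary endpoint rate was 55% in this historical group". No split by patient type is given.
- **Sites.** The controls come from one centre. Section 4.1 allows Washington University and up to five further sites for the treated patients.
- **Adjustment elsewhere.** In Section 9.2, Cox models for patient characteristics sit with the time-to-event endpoints, logistic regression serves the ADAMTS13 biomarker question, and Cochran-Mantel-Haenszel serves rituximab levels and B cell depletion. None of them adjusts the primary comparison.
- **Data available.** Section 6.1.3 records "History of TTP" at baseline.

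**The concern.** Nothing in the design balances the two groups. Meeting the same entry criteria does not give them the same composition, because the criteria span two kinds of patient. A single-centre control series and a treated group from up to six sites may hold different proportions of relapsed patients.

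Bias in the pooled test needs two things together: a composite rate that differs by patient type, and a mix that differs by group. With both present, the treated rate moves away from the control rate without any drug effect. Depending on the signs, this either produces an apparent benefit or conceals a real one. The primary result of the pilot could then not be separated from case mix, on a variable the protocol already uses to define entry.

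**Working it through.** **1. The plan's own figure.** Inputs from Section 9.1: 55% in 40 controls, 10% in treated, 5% significance (sidedness not stated; two-sided assumed), 14 treated for 90% power. Normal approximation with pooled variance:
- pooled rate = (14 × 0.10 + 40 × 0.55)/54 = 0.433
- null standard error = √[0.433 × 0.567 × (1/14 + 1/40)] = 0.154
- alternative standard error = √[0.10 × 0.90/14 + 0.55 × 0.45/40] = 0.112
- power = Φ[(0.45 − 1.96 × 0.154)/0.112] = 90.7%

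The 14 reproduces. With the planned two-sided Fisher test, exact enumeration gives 84.2% at 14 and 94.8% at the 20 to be enrolled. The calculation treats each group as homogeneous.

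**2. How far a difference in mix moves the treated rate.** With no drug effect, shift = (rate gap between types) × (difference in the proportion of one type).

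Assumed, because the documents give no values: controls 27 newly diagnosed and 13 relapsed (67.5%/32.5%), with type-specific rates chosen to keep the control rate near 55%. Example with 65% newly diagnosed, 35% relapsed and treated 7/13:
- controls: 0.675 × 65% + 0.325 × 35% = 55.25%
- treated: 0.35 × 65% + 0.65 × 35% = 45.5%
- shift: 0.30 × (0.675 − 0.35) = 9.75 points

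On the observed scale, against 22/40 a treated result of 5/20 gives Fisher p = 0.032 and 6/20 gives p = 0.100. Significance therefore needs much less than the planned 45-point difference.

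**3. False significant benefit with no drug effect** (20 versus 40, two-sided 5% pooled Fisher, rejections favouring rituximab; the nominal ceiling is 2.5%):

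| Assumed rates, newly diagnosed/relapsed | Treated mix | Shift in treated rate | Pooled Fisher |
|---|---|---|---|
| 65%/35% | as controls (nearest 13/7) | about 0 | 1.4% |
| 65%/35% | 10/10 | −5.25 points | 3.0% |
| 60%/45% | 7/13 | −4.9 points | 3.3% |
| 65%/35% | 7/13 | −9.75 points | 6.0% |
| 45%/75% | 7/13 | +9.75 points | 0.15% |

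In the 6.0% scenario, an exact conditional stratified test gives 1.9%. A harsher assumption (controls 36/4 and treated 10/10 in higher-risk/lower-risk type, 40-point gap) gives 13.2% pooled and 1.8% stratified.

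**4. A hidden effect.** Take 45%/75% and a common odds ratio set so that the treated rate at the control mix would be 25%. That odds ratio is about 0.244, which makes the treated rates 16.7% and 42.3%. Check: 0.675 × 16.7% + 0.325 × 42.3% = 25%. With treated 7/13 the treated rate becomes 0.35 × 16.7% + 0.65 × 42.3% = 33.3%. Power is about 26% pooled and 56% stratified.

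**5. Price of stratifying.** With 65%/35%, the same mix in both groups and a treated rate near 10%, power is about 95% pooled and 96% stratified. With treated 7/13 and the same odds ratio, it is about 98% pooled and 90% stratified. The 98% is inflated by the confounding.

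**The case against.** The strongest reply is that the size is speculative. The documents give no composite rate by patient type and no mix. If treated patients were drawn from a population with the assumed control mix, 7 or fewer newly diagnosed out of 20 would occur with probability 0.3%, so the 6.0% case needs a systematic shift as well as a large gap. At a 10-point gap even the 7/13 mix gives only 2.6%. This is also a 20-patient pilot, and era, site, severity and inhibitor titre could confound as much as patient type. All of this stands. It limits the size of the point but does not answer it: matching on eligibility leaves the mix open, and multi-site recruitment against one-centre controls makes some shift plausible.

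Two stronger readings should be resisted.
- A reader might infer that the different platelet ceilings themselves bias the test, because relapsed patients can start nearer the response threshold of 150,000/µL. Both ceilings apply to both groups, and they are upper limits rather than observed counts. They mark two patient types and no more.
- A reader might infer that extra relapsed patients in the treated group would favour rituximab. No section supports that direction. Section 2.1 links ADAMTS13 inhibitors with relapse, delayed response and refractory disease, which could point the other way but does not establish composite rates by type either.

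**Conclusion.** The point holds as a design weakness of unknown sign and size. The primary comparison is unadjusted, the controls are matched on eligibility only, and no planned analysis would show whether patient type explains the result.

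Under the main assumed scenarios, pooled false benefit runs from 0.15% to 6.0%, against about 1.4% with equal mixes. Material inflation needs both a large rate gap and a large shift in mix. Mix alone could hardly create the full planned difference, since gap × mix difference would have to reach 0.45. It could carry a borderline result across the significance line, or hide a moderate effect. All type-specific rates and mixes here are assumptions. The remedy is justified because it is cheap, not because bias has been shown.

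**What to change.** 1. Classify all treated patients and the 40 controls as newly diagnosed or relapsed, by one written rule applied identically to both groups, before outcomes are compared.
2. Tabulate the mix and the composite rate by type in both groups.
3. Pre-specify in Section 9.2 an exact stratified (conditional Mantel-Haenszel) test of the composite with these two strata. Make it the primary test or, at minimum, a key sensitivity analysis reported beside the pooled Fisher test. If it is primary, keep the pooled Fisher result as the sensitivity analysis.

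The cost is one extra field from the control charts and a change of SAP wording; the treated patients' history is already collected. Power is essentially unchanged if the mixes agree and falls if they differ (about 90% with treated 7/13 in the scenario above). Other biases of a historical control group remain.
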